robust and widely used pulse sequence for intrinsic connectivity modeling. BOLD images will be used for computing treatment plans and for testing for intrinsic connectivity changes by symptom score and with treatment. BOLD data will be acquired as 360 whole-brain volumes acquired with a TR = 2500 ms, TE = 30 ms, tip angle = 90°, 128 x 128 voxels, 1.7 mm x 1.7 mm, and 36 slices (4.0 mm thickness). This sequence requires ~ 15 minutes. Resting-state BOLD (15-min acquisition) will be used to map per-subject the voxel-wise intrinsic connectivity of DLPFC with the anterior cingulate cortex (ACC) and Precuneus; this will guide aiming parameters.

Motor Threshold Assessment. After the baseline MRI session, each patient will undergo a brief motor threshold assessment by single pulse TMS to their primary motor cortex hand region which elicits a contraction of the targeted hand muscle. The motor threshold assessment begins by locating the hand region and applying single pulses of TMS—with at least 5 seconds between successive pulses—at increasing levels of TMS intensity. We continue to ramp up the TMS intensity with each TMS pulse until we observe a contraction of the targeted hand muscle in 5 out of 10 pulses at a given TMS intensity. This TMS intensity will then be recorded as that patient's resting motor threshold. Using the patient's BOLD fMRI of the primary motor cortex, we can calculate their coil-to-cortex depth and use this information to determine the correct irTMS treatment intensity for the DLPFC and also determine the correct train duration needed to safely deliver 20Hz irTMS in each patient using published safety guidelines on appropriate train durations at specific TMS frequencies and intensities.

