Post-treatment MRI. Immediately following the last irTMS treatment at the end of the 3rd week, a second functional MRI scan will be conducted to assess treatment effects. The post-MRI will occur any time after last treatment with up to a 3-day window for completion. In rare instances, if scheduling circumstances (such as weekends and institution holidays, MRI staff outages, participant discharge date) prevent the post-MRI from occurring after all treatment sessions have been completed, the post-MRI may be conducted before the final treatment session, and any remaining treatment sessions will occur after the post-MRI. This will be documented in the participant study file and will be considered during data analysis. After the post-treatment MRI session, each patient will also undergo another brief motor threshold assessment in order to document any changes which may be used to report on the safety of this TMS treatment protocol. This second scanning visit should take approximately 1 hour.

Participant Blind Form. The Participant Blind Form measures the participant's best guess about the study treatment that they received, level of confidence in this guess, and how unblinding could potentially have occurred. This form will be used at treatment completion and follow-up for all CAP RCTs that are double-blind (i.e., medication studies).

Independent Evaluator Blind Form. The Independent Evaluator Blind Form measures the independent evaluator's best guess about the study treatment that the subject received, level of confidence in this guess, and how unblinding could potentially have occurred.

Phase III: 1 Month/3 Month Follow-Up

One month and three months after the final iTMS treatment session, participants will be interviewed (either in-person or over the telephone) by a member of the research team. Self-report measures may be administered over the phone or by direct electronic data capture via a secure link to the secure STRONG STAR database.

Table of Study Procedures:

Phase	Pre-Study (at LRTC)			3 Week Treatment (at LRTC & the RII)			Post-Treatment (at the RII)	1 Month/3 Month Follow-Up (either in-person or via telephone)
	Wk 0			Wk 1	Wk 2	Wk 3	Wk 3	Wk 7/Wk15
	LRTC Intake	Baseline	MRI Appt					
	Day(s)	0 to 1	1-3	2-3	7	14	20	21 -24
Medical History	X							
Metal Screening		X						
Informed Consent		X						
1. Demographics & Military Service Characteristics		X						
2. History of Head Injuries Screening		X						

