3. Clinician-Administered PTSD Scale for DSM-5 (CAPS-5)		X						X
4. PTSD Checklist for DSM-5 (PCL-5)		X		X	X	X		X
5. Life Events Checklist - 5 (LEC-5)		X						X
6. Deployment Risk and Resiliency Inventory-2 (DRRI-2) Combat and Postbattle Experiences Subscales		X						
7. Patient Health Questionnaire-9 (PHQ-9)		X		X	X	X		X
8. 'Structured Interview Guide for the Montgomery-Åsberg Depression Rating Scale (SIGMA).pdf'		X				X		X
9. Generalized Anxiety Disorder Screen (GAD-7)		X		X	X	X		X
10. Alcohol Use Disorders Identification Test (AUDIT) self-report version		X						X
11. Quick Drinking Screen (QDS) self-report version		X						X
12. Fagerstrom Test for Nicotine Dependence		X				X		X

13. Fagerstrom Test for Nicotine Dependence – Smokeless Tobacco		X				X		X
14. Insomnia Severity Index (ISI)		X				X		X
15. Snoring, Tired, Observed, Blood Pressure (STOP) Sleep Apnea Screen		X						
16. Patient Reported Outcomes Measurement Information System (PROMIS) Sleep Disturbance and Sleep-Related Impairment short forms		X				X		X
17. Depressive Symptoms Index – Suicidality Subscale		X				X		X
18. Self-Injurious Thoughts and Behaviors Interview short form		X				X		X
19. Veterans RAND 12-Item Short Form Health Survey (VR-12)		X						X
20. Brief Inventory of Psychosocial Functioning (B-IPF)		X						X
21. Health Questionnaire		X				X		X
22. Clinical Global Impressions (CGI)		X				X		X
Adverse Events Monitoring			X	X-X	X-X	X-X		X
Concomitant Medications/Treatment	X-X	X-X		X-X	X-X	X-X		X
Structural MRI			X					
Intrinsic Connectivity by Blood-Oxygen-Level-Dependent Functional MRI			X				X	
Motor threshold assessment			X				X	
irTMS Treatment (20 consecutive days)				X-X	X-X	X-X		
Participant Blind Form							X	
Independent Evaluator Blind Form								X

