- Rare and Serious. In 100 people, approximately 1-2 may have:
 - Seizures

Risks and Side Effects related to the Robot placement of the iTMS include those which are:

- Rare and Serious. In 100 people, approximately 0-1 may have:
 - Physical injury from the robotic device.

Risks and Side Effects related to the MRI include those which are:

- Rare and Not Serious. In 100 people, approximately 1 may have:
 - Claustrophobia (fear of tight spaces). During the MRI scan, participants will be asked to remain perfectly still.
- Rare and Serious. In 100 people, approximately 1-2 may have:
 - Foreign bodies which may interact with the magnetic field of the MRI

Risks related to the Psychological Assessments include those which are:

- Less likely (less than 5-20 subjects out of 100) and Not Serious:
 - Emotional distress including experiencing an initial increase of PTSD symptoms due to the discussion of traumatic events.
- Rare (less than 5 subject out of 100) and Serious:
 - Breach of confidentiality.

Risks of having a diagnosis of PTSD regardless of participation in this research or not: Individuals with PTSD may have suicidal thoughts or attempt suicide. This is a risk to you whether you are being treated for PTSD or not. Therefore, the risk of suicide is not any higher in the study than it would be if you were not in this study.

Risk Minimization.

- To physical injury by the robotic device. Robotic devices must be used with caution in the presence of persons. The robotic device used here (KUKA®) poses no significant risk. The KUKA® moves slowly, so that it can easily be stopped prior to any collision. Loss of electrical power renders the KUKA® robot immobile in its current position, (i.e., it does not return to a “parking” position or make any sudden motions). The KUKA® robot requires a key and a recessed button to actuate, being used only under direct supervision. Collectively, these features make the KUKA® robot safe for use by and with humans.
- To claustrophobia in the MRI.
- To injury during the MRI from foreign bodies interacting with the magnetic field. MRI can have risk for persons with foreign bodies implanted in their body. Cardiac pacemakers and cochlear implants may cease to function and can be permanently damaged by the MRI. Surgical clips on aneurysms and intestines may be moved by the magnetic field. Ferrous metal filings in the eye (e.g., in machinists) can be

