Clinical Outcomes Data Analysis plan. All pre-treatment and post-treatment MRIs will be acquired and analyzed at the RII, however, all of the statistical analysis of the symptom scores for this project will be done upon completion of recruitment and termination group blinding. The primary efficacy outcome measure will be the PTSD Checklist (PCL-5) for symptoms assessed pre-treatment, weekly during treatment, post-treatment, and 1-month following the completion of treatment and the Clinician-Administered PTSD Scale for DSM-5 (CAPS-5) for the diagnosis of PTSD assessed pre-treatment and 1-month following the completion of treatment. The primary analysis will use mixed effects regression models. Secondary analysis will focus on changes in PTSD symptoms clusters, effects of the intervention in mood symptoms, functioning and cognitive outcomes. Types and rates of adverse events will be summarized and compared across the study groups. The durability of benefit and the clinical significance of PCL changes will be explored. Non-compliance to protocol as defined as missing two consecutive iTMS sessions or receiving less than 16 iTMS sessions during hospitalization at LRTC will be assessed for and evaluated in data analysis.

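### No adverse-event enquiry is scheduled at the Post-Treatment visit (Days 21-24), so the next planned one comes about three to four weeks later

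*Combined protocol and SAP*

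**What the plan says.** The schedule is in Item 6, Table of Study Procedures. The row "Adverse Events Monitoring" carries a mark at the first MRI appointment, in each of the three treatment weeks and in the combined 1-month/3-month follow-up column. The cells for intake, baseline and Post-Treatment are empty.

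The Post-Treatment column is not an empty visit. The functional MRI row and the row "Motor threshold assessment" are both marked there, as is the Participant Blind Form. The Post-treatment MRI paragraph sets the timing: "The post-MRI will occur any time after last treatment with up to a 3-day window for completion". It continues: "After the post-treatment MRI session, each patient will also undergo another brief motor threshold assessment in order to document any changes", and adds that these changes may feed a safety report on the TMS protocol. The Motor Threshold Assessment paragraph describes the baseline version of the procedure as a "brief motor threshold assessment by single pulse TMS to their primary motor cortex hand region which elicits a contraction" of the target hand muscle. No sham version is described.

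Two other places bear on the point. The paragraph on adverse events, unanticipated problems and deviations says that adverse events are assessed under STRONG STAR and CAP SOPs and IRB policy, without naming visits. The Clinical Outcomes Data Analysis plan states: "Types and rates of adverse events will be summarized and compared across the study groups".

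**The concern.** At the first MRI appointment the schedule asks for adverse events even though the concomitant-medication row is blank there. The mark therefore seems to follow the procedures done that day, namely MRI and motor-threshold pulses. Both recur at Post-Treatment, but the mark does not, and no reason is given. This looks like an omission.

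Two kinds of event are affected. The first is anything that follows the second MRI or the second set of motor-threshold pulses. The second is anything that appears after the final irTMS session, since this is normally the first study contact after it. The protocol expects headache, scalp or facial pain, twitching or neck pain in about 20-30 of 100 people over a course of irTMS. Events of that kind are usually mild and short-lived, and are easily forgotten if nobody asks for several weeks. At stake is how complete the adverse-event summary is for the end of treatment, at a visit whose motor-threshold results are themselves meant to inform safety.

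**Working it through.** The plan gives no figure for this interval, so there is none to reproduce. The check has three parts.

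**1. Is the blank cell real?** The table was read from PDF, so a shifted column has to be ruled out. Reading each row against the eight visit columns gives:

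| Row | Columns marked |
|---|---|
| Adverse-event monitoring | MRI appointment, Wk 1, Wk 2, Wk 3, follow-up |
| Motor threshold | MRI appointment, Post-Treatment |
| Functional MRI | MRI appointment, Post-Treatment |
| Participant Blind Form | Post-Treatment |
| CAPS-5 | Baseline, follow-up |
| Independent Evaluator Blind Form | Follow-up |

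The comparison rows fall where the text leads one to expect, so the alignment is sound and the Post-Treatment cell of the adverse-event row is empty.

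**2. How long until the next scheduled enquiry?** Inputs from the table header: last treatment day marked, Day 20; Post-Treatment, Days 21-24; first follow-up, Wk 7. Input from the follow-up paragraph: one month after the final session, in person or by telephone.

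- Week 7 runs from Day 6 × 7 + 1 = 43 to Day 7 × 7 = 49.
- Shortest gap from the visit: 43 − 24 = 19 days.
- Longest gap from the visit: 49 − 21 = 28 days.
- From Day 20 to the end of Week 7: 49 − 20 = 29 days.
- Alternative reading, with one month as 30 days after a last session on Day 20: follow-up falls on Day 20 + 30 = 50, so the gap from the visit is 50 − 24 = 26 to 50 − 21 = 29 days.

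On either reading the gap is roughly three to four weeks.

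**3. How does the Baseline blank compare?** Baseline is on Days 1-3, and the MRI appointment, which does carry an adverse-event mark, is on Days 2-3. The gap is 0 days at least and 3 − 1 = 2 days at most.

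The number of participants affected is those who reach the Post-Treatment visit. The plan aims for 100 completers (50 per arm) out of 132 randomized. The documents give no basis for estimating how many events a missing enquiry would lose.

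**The case against.** The best reply is that the protocol has a general rule. Adverse events are handled under outside SOPs and all are reported to the IRB. Those SOPs are not in the documents and may require a check at every contact. Serious interval events also have another route, because the follow-up Health Questionnaire asks about emergency care and hospital stays. This stands as a limit: one cannot infer from a blank cell that events at this visit go unrecorded. It does not close the gap, because the general rule names no visit and the table is the only visit-level statement.

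The procedures are also low in risk. No risk is listed for single-pulse motor-threshold testing. The listed MRI risks are about 1 in 100 for claustrophobia and 1-2 in 100 for foreign bodies, and they would probably show during a staffed scan in people who have already had one. That is fair, and it shifts the weight of the point to late events after irTMS. Day 20 itself is covered by the Week 3 mark. In the rare case where the second MRI precedes the last session, monitoring resumes at that session.

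Two stronger readings are tempting, and the documents support neither.

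- A reader might infer that the Baseline blank does the same harm, since the protocol lists "experiencing an initial increase of PTSD symptoms due to the discussion of traumatic events" as a risk of psychological assessments. It does not: an adverse-event mark follows within 0 to 2 days, before the first irTMS session, and interviews are stopped if the subject is distressed.
- A reader might infer that the gap biases the comparison between arms. The second MRI and the motor-threshold pulses are planned identically in both arms, so events they cause are common background. The blank cell applies to both arms alike, and no directional effect is shown.

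**Conclusion.** The point holds as a small, specific gap in scheduled ascertainment. The Post-Treatment visit repeats the two procedures done at an earlier visit where enquiry was scheduled, and is normally the first contact after irTMS ends, yet nothing is scheduled there. The next planned enquiry is 19-28 days after the visit, or up to 29 days after Day 20. The likely effect is some under-recording of mild or transient late events in both arms, of unknown size.

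This assumes that the table's day numbers apply, that the last session falls on Day 20, that Week 7 means Days 43-49 (or one month means 30 days), and that sites follow the table where the SOPs are silent. If the SOPs already require a check at every visit, what remains is an inconsistency in the table, which still needs correcting.

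**What to change.** Mark adverse-event monitoring in the Post-Treatment column. Reconcile the table with the adverse-event paragraph by stating at which visits enquiry is made and what the SOPs add. For each event, note whether it followed an irTMS session, the MRI or the motor-threshold pulses, so that attribution is clear in the summary.

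The cost is one mark in the table, a sentence of text and a few minutes at a visit that already takes place and already includes a participant form.

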Random Assignment. Prior to the Treatment Phase, participants will be randomly assigned using a statistically generated randomization program to 1 of 2 active irTMS treatment arms. An irTMS treatment plan will be developed specifically for each participant, which will be securely-transmitted to the irTMS treatment team at the LRTC. The master list of treatment arm enrollment will be securely-stored (i.e. password-encrypted) on UTHSCSA's XNAT server and will not be available to members of the research team until all of the participant's treatment sessions and symptom assessments have been completed. Therefore, all members of the LRTC's irTMS treatment team will be blinded to which treatment arm each participant is assigned. irTMS treatment visits will take place at the LRTC immediately following the Baseline scan and development of the treatment plan.

Phase II: 3-Week Treatment Phase.

irTMS Treatment Planning. All irTMS treatments will be planned for robotic, image-guided irTMS delivery—which will be performed at the LRTC. The acquired MRI images will be used to compute a patient-specific, treatment plan, which will be stored and used during their respective irTMS session at the LRTC. Image guidance will be based on treatment plans developed from high-resolution structural MRI and resting-state BOLD fMRI acquired at the RII. From the T1-weighted MRI (described above), two surface models are computed: a model of the scalp surface, for use in registration of the patient to the treatment plan; and, a model of the cortical surface including cortical surface normals. Both models are created using a modification of the dividing cubes algorithm following automated tissue segmentation. The scalp surface model is based on the air-scalp interface, which is readily obtained by simple thresholding. The cortical surface model is based on pre-classification of brain tissue into gray, white and CSF surfaces, using the FMRIB's Automated Segmentation Tool.

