The right DLPFC treatment target locations will be based on connectivity strength with ACC and Precuneus using region-seeded resting-state BOLD fMRI. Coil orientation will be corrected for the underlying gyral anatomy, using a T1-MRI derived cortical surface model to align the E-field according to the cortical column cosine model. Stimulation intensity will be corrected for the distance of the stimulation site from the scalp/coil surfaces. Intensity ranges will be individually adjusted for each patient—to deliver depth-corrected E-fields between 80 volts/meter and 95 volts/meter.

Sham TMS: An image-guided treatment plan will be computed for sham TMS subjects in the same manner as for active irTMS to ensure therapist blinding.

irTMS Treatment Sessions. All participants will continue with their TAU at LRTC (or its treatment clinics) including regular medication management encounters with their attending psychiatrist and therapy sessions as of their treatment. An effort will be made to limit the disruptions in patients' TAU by working research assessments and irTMS around their expected TAU programming. irTMS treatment visits will take place at the LRTC starting as soon as possible after the treatment plan is completed, expected to be 1-2 working days following baseline scanning.

irTMS Position/Holding. For each subject, the coil pose will be pre-computed from structural and functional MRI and stored as an individualized treatment plan. Each subject's treatment plan will be registered to his/her head by creating a scalp model with a high-resolution digitizer, an integrated component of the irTMS system. In each arm,

the TMS coil will be positioned and held by the robot (under the treatment technician's supervision).

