irTMS Treatment Protocol. At the respective TMS treatment target site, the LRTC team will deliver irTMS using an irTMS treatment protocol of PTSD which falls within the previously published safety guidelines for TMS treatments. This TMS protocol consists of 1,600 irTMS pulses per session, delivered at a frequency of 20 Hz. Intensity ranges (designed to deliver depth-corrected E-fields of 80-95 volts/meter) will be determined when the patient's treatment plan is developed and these intensity ranges will be given to the treatment technicians with the irTMS treatment plan. On the first day of the irTMS treatment, the patients will be given brief trains of TMS pulses beginning at 95 volts/meter of intensity. If that level of intensity causes discomfort or significant levels of facial muscle twitching, the intensity will be adjusted downward in 5 volt/meter units (i.e., 90, 85, 80 etc.) until a level is found within the 80-95 volts/meter range. That final intensity will be used throughout the remaining treatment phase for that patient. If study participants decide that they cannot tolerate the lowest prescribed dose of irTMS (e.g. 80 volts/meter), they will be withdrawn from the study (see Discontinuation and Withdrawal of Patients Section below).

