TMS treatment guidelines recommend that the train duration of TMS pulse protocols remain within the limits of published safety guidelines (reached by a consensus of TMS practitioners). For example, if a patient requires a TMS intensity equivalent to 130% of their motor threshold, then we must limit our TMS train durations to 0.55 seconds (i.e. 11 pulses/train). Therefore, we will adjust the train duration of each patient's treatment protocol so that it falls within the limits of these recommendations. We will also adjust the intertrain interval to ensure that we deliver all of our treatment pulses within the hour-long treatment session. For example, if a patient needs a TMS intensity equivalent to 130% of their resting motor threshold, we will deliver 160 pulse trains of irTMS (e.g. train duration = 0.5 seconds; intertrain interval = 7.5 seconds; 10 pulses per train), which would require 21.33 minutes of treatment time to deliver the desired number of TMS pulses in each session (i.e. 1,600 pulses). The primary TMS treatment parameters (TMS frequency (i.e. 20Hz), number of pulses per session (i.e. 1,600), and number of sessions (i.e. 20) will remain the same across patients. We may only adjust the patient's intensity and the protocol's train duration and intertrain intervals so that they fall within the safety limits of repetitive TMS treatments.

Active treatment will use a liquid cooled figure-8 MagPro coil (MagVenture, Denmark). Sham treatment will use a coil that simulates the sound and scalp stimulation of TMS but does not deliver an E field (MagVenture, Denmark).

Participants will receive treatment 7 days per week for as long as they are hospitalized at LRTC for up to 20 sessions. On each treatment day, a total of 1,600 pulses will be administered within the one hour TMS session. With the set up for treatment, the total time required for each treatment visit should be less than one hour per day. This protocol will administer a total of 24,000 pulses over the three-week period. If study participants decide, at any time, that they cannot tolerate the irTMS treatments, they will be withdrawn from the study (see Discontinuation and Withdrawal of Patients Section below) and will be assisted in finding appropriate after-study care.

Phase II: Post-Treatment Follow-Up

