moved by the magnetic field. Foreign body risk is minimized by including only volunteers with no known foreign bodies and no exposure to circumstances, which might predispose to foreign bodies (e.g., metal machine workers). Before receiving an MRI, participants will be asked about any metal objects that may be in their body.

- To emotional distress during psychological assessments. All clinical staff associated with assessment have experience in psychiatric evaluation and will implement protocol procedures in a sensitive and supportive manner. Interviews will be stopped if subjects become distressed or object to answering questions. Measures implemented to minimize risks are: 1) Before participating, subjects undergo careful psychiatric and medical evaluation. 2) An experienced study clinicians are available at all times during the sessions to provide medical a psychiatric monitoring for subjects experiencing any difficulties during treatment. 3) All subjects will be seen weekly for ongoing assessment of behavioral symptoms. 4) If a subject's clinical condition significantly worsens, he or she will be withdrawn from the research protocol to continue TAU at LRTC. Any indication that a participant's suicidality has worsened from baseline will be handled using processes at the LRTC.
- To breach of confidentiality. Study participants will be treated in individual offices located on the LRTC. Data a will be stored by an assigned participant code number so that data records and specimens can be viewed by password-authenticated, authorized investigators and Consortium personnel. Digital audio recordings of assessments will be labeled with the participant's study id number and saved on a secure password protected server. Those recordings to be reviewed for fidelity to ensure that the assessment is being delivered in accordance with Consortium standardized procedures. There is no option for the reviewers to download or otherwise save the recordings to their computers. Every member of the Research Team will be trained and monitored about how to handle and protect both medical and research records. Only authorized study staff, and members of the Data Management and Biostatistics Core will have access to either the raw data or electronic study data.

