Discontinuation of Subjects. Subjects may be discontinued from study treatment and assessments at any time. Specific reasons for discontinuing a subject from this study are: 1) Voluntary discontinuation by the subject, who is at any time free to discontinue his/her participation in the study without prejudice to further treatment; 2) Clinical deterioration: The following are objective criteria for clinical deterioration, (a) a 25% increase in the PCL-5 at any time during the study, (b) Patients with a CGI-I score ≥ 6 at any post-baseline visit, and (c) the onset of active suicidality as assessed by the study clinicians requiring treatment outside of the study protocol; 3) Evidence of intolerable adverse reaction, or unable to tolerate iTMS or MRI; 4) Safety reasons as judged by the investigator.

Potential Benefits.

- The potential benefit to participants is the potential for PTSD and/or depressive symptom relief.

Adverse Events, Unanticipated Problems, and Deviations.

Adverse Events will be assessed and monitored according to the established STRONG STAR and CAP SOPs and the IRB of record's policies and procedures. Reporting Adverse Events, Unanticipated Problems Involving Risks to Subjects or Others (UPIRSOs), and Deviations to the Office of the IRB. All adverse events, unanticipated problems involving risk to subjects or others, and deviations will be reported to the Institutional Review Board (IRB) in accordance with current IRB policy. UPIRSOs and recurrent non-compliance with study procedures will be reported promptly to the IRB. All adverse events that do not meet the UPIRSO criteria and deviations that are not non-compliance will be summarized at Continuing Review per the IRB of record's policy.

Research Monitor.

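### Randomised participants withdrawn for irTMS intolerance or clinical worsening leave the study, and no PCL-5 or CAPS-5 is planned for them afterwards

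*Combined protocol and SAP*

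**What the plan says.** Timing: under Random Assignment (Item 6), "Prior to the Treatment Phase, participants will be randomly assigned using a statistically generated randomization program". Every withdrawal during treatment is therefore of a randomised participant.

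Intolerance: irTMS Treatment Protocol has two rules. At the first-day titration, "If study participants decide that they cannot tolerate the lowest prescribed dose of irTMS (e.g. 80 volts/meter), they will be withdrawn from the study". Later, "If study participants decide, at any time, that they cannot tolerate the irTMS treatments, they will be withdrawn from the study"; the only follow-on offered is help with finding care after the study.

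Worsening: under Risk Minimization, a subject whose condition significantly worsens leaves, in these words: "he or she will be withdrawn from the research protocol to continue TAU at LRTC".

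Scope: Discontinuation of Subjects opens with "Subjects may be discontinued from study treatment and assessments at any time". Its listed reasons include clinical deterioration (a 25% rise in PCL-5, a CGI-I score of 6 or more, or new active suicidality) and "Evidence of intolerable adverse reaction, or unable to tolerate iTMS or MRI". It describes no later assessment.

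Outcomes: the Clinical Outcomes Data Analysis plan names PCL-5 (pre-treatment, weekly, post-treatment, 1 month) and CAPS-5 (pre-treatment, 1 month) as primary, analysed by mixed effects regression. It states no analysis set, no missing-data method and no rule for outcomes after withdrawal. The Table of Study Procedures has no early-termination visit.

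**The concern.** Two of the exit routes are tied to the treatment or the outcome: tolerability of stimulation, and worsening, one of whose triggers is a primary outcome itself. If outcome collection ends when irTMS ends, the missing data arise after randomisation for reasons that may relate to arm and to prognosis. The comparison of everyone as randomised then depends on an untestable assumption about what happened to the leavers, and data not collected cannot be recovered at analysis.

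The point does not extend to participants who stay in the study but miss sessions. The analysis plan defines non-compliance (two consecutive missed sessions, or fewer than 16 in all) and says it will be evaluated.

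**Working it through.** **1. The plan's own figure.** Step-by-Step Methods randomises 132 (66 per arm) to retain 100 completers (50 per arm). No dropout rate is stated. The implied rate is 1 − 50/66 = 24.2%, or 32 of 132; an assumed 24% gives 50/(1 − 0.24) = 65.8, rounded up to 66. This allowance covers all causes up to the end of treatment. The part due to intolerance or worsening is not given.

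**2. What each kind of leaver would have on record.** After baseline, the procedures table schedules PCL-5 at Days 7, 14 and 20 and at follow-up, and CAPS-5 only at follow-up.

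| Leaver | PCL-5 on record | CAPS-5 on record |
|---|---|---|
| Intolerant at first-day titration | Baseline only | Baseline only |
| Intolerant later | Baseline plus any weekly scores already taken | Baseline only |
| 25% PCL-5 rise during treatment | Baseline plus at least the triggering score | Baseline only |

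A likelihood-based mixed model can use the triggering score under missing at random, so the PCL-5 concern is smaller for the third group. It has no post-baseline CAPS-5 to use for any of them.

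**3. Bias for first-day leavers.** Let p be the proportion leaving in an arm, and g the number of points by which leavers end up worse at 1 month than stayers with the same baseline. With A for active and S for sham, the mean over all randomised is the stayers' mean plus p × g. A model that sees only baseline for leavers estimates the stayers' contrast, so

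overstatement of benefit = pA·gA − pS·gS.

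All values of p and g are assumptions. A simulation checked the formula (66 per arm, 3,000 runs; assumed SD 14, equal correlation 0.6, stayers' effect −5, common baseline; Monte Carlo SE of the bias at most 0.02).

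| Leaving, active / sham | g | Formula (points overstated) | Simulation |
|---|---|---|---|
| 5% / 0 | 5 | 0.05 × 5 = 0.25 | 0.26 |
| 5% / 0 | 10 | 0.05 × 10 = 0.5 | 0.49 |
| 10% / 0 | 10 | 0.10 × 10 = 1.0 | 1.01 |
| 20% / 0 | 10 | 0.20 × 10 = 2.0 | 2.01 |
| 20% / 10% | 10 | 2.0 − 1.0 = 1.0 | 1.02 |
| 15% / 15% | 10 | 0 | 0.00 |
| 0 / 20% | 5 | −1.0 (understated) | −0.99 |

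Of 66 per arm, 5%, 10% and 20% are about 3, 7 and 13 people.

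**4. Precision.** If all 32 planned losses left with baseline only, the SE of the 1-month contrast relative to full follow-up is √[(1/nA + 1/nS)/(2/66)], where nA and nS are the numbers remaining.

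| Leavers, active / sham | Remaining | SE ratio to 66/66 | Ratio to planned 50/50 |
|---|---|---|---|
| 16 / 16 | 50 / 50 | 1.149 | 1.000 |
| 24 / 8 | 42 / 58 | 1.164 | 1.164/1.149 = 1.013 |
| 32 / 0 | 34 / 66 | 1.213 | 1.213/1.149 = 1.056 |

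The 1.149 is √(132/100), which the sample size already allows for. The extra inflation is 0%, about 1% and about 6%.

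**The case against.** The strongest reply is that silence is not loss. The opening sentence of Discontinuation of Subjects is permissive, and the sections that order withdrawal do not forbid later assessment. Three general statements could be read as covering everyone: the CAPS-5 description refers to all participants, Phase III times its interviews from the last session (which an early leaver also has), and Risk Minimization says all subjects are seen weekly. Consent pages and the Assessment Core procedures are not available to check.

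Part of this stands. A reader might infer that the data will certainly be lost; the documents support only that their collection is not planned or assured. But the general statements do not answer the point. The CAPS-5 text is an instrument description that also addresses other consortium studies. The weekly-contact item is followed directly by the one withdrawing worsening subjects. None of the three mentions people who have been withdrawn.

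A reader might also infer a bias in favour of active treatment, since only the active coil delivers an E field. The documents do not support that. The sham coil "simulates the sound and scalp stimulation of TMS but does not deliver an E field", the dose is stepped down before anyone is withdrawn, and no rates by arm are given. Nor should the 32 allowed losses be read as 32 withdrawals for intolerance or worsening, or the 15% SE inflation as a new cost.

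**Conclusion.** The gap holds as a matter of text: randomised participants leave for reasons linked to treatment or outcome, treatment and assessments may stop together, and no later PCL-5 or CAPS-5 is planned. It is most serious for first-day intolerance (PCL-5) and for anyone withdrawn during treatment (CAPS-5), and milder on PCL-5 for those withdrawn on a PCL-5 rise.

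The consequence is conditional. Bias requires both that leaving or the leavers' deficit differs by arm and that leavers differ from stayers; its sign is unknown. The figures of 0.25 to 2.0 PCL-5 points are illustrations for first-day leavers only, with no input from the documents. The largest needs 13 of 66 to leave active, none to leave sham, and a 10-point deficit. At 5% leaving active only, the bias is 0.25 to 0.5 point, or 0.02 to 0.04 of the assumed SD of 14. Loss of precision beyond what was planned is at most about 6% under the splits examined. The point should be fixed because prevention is cheap. Confidence is high on the omission, not on the size of its effect.

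**What to change.** - In irTMS Treatment Protocol, Risk Minimization and Discontinuation of Subjects, separate stopping irTMS from stopping assessments. Leave the clinical criteria for stopping irTMS unchanged.
- Keep every randomised participant on the PCL-5 and CAPS-5 schedule unless consent is withdrawn, or the study clinician or Research Monitor judges an assessment unsafe; record the reason in either case. The safety exception is needed because some leave for active suicidality, and distress from assessment is a listed risk.
- Collect on site while the participant is on TAU. The irTMS Treatment Sessions section says "All participants will continue with their TAU at LRTC (or its treatment clinics"), and worsening participants also remain in TAU there. After that, use the telephone interview, and the telephone or electronic self-report, already provided in Phase III.
- In the Clinical Outcomes Data Analysis plan, state that the primary analysis includes all randomised participants as assigned, with data collected after irTMS stops.

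The cost is protocol and consent wording, plus extra assessments for at most about 32 participants if loss is as planned (more if it is higher), using existing assessors. The estimated effect may become smaller or larger as a result.
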